125 transplant clinical personnel participants will be recruited from the International Society for Heart and Lung Transplantation (ISHLT) and the Pediatric Heart Transplant Society (PHTS). Participants will be recruited via (1) the ISHLTConnect Discussion Board webpage, (2) the PHTS Basecamp Discussion Board webpage and corresponding Listserv, and (3) the PHTS July 2020 Live Webinar (via Zoom). Inclusion criteria: Participants who are transplant clinical personnel will be asked to participate if they confirm the following inclusion criteria in the consent form. (1) 18 years of age or older (2) must read and understand the information in the consent form (3) must want to participate in the research and continue with the survey Payment: Participants will be given the option to select a transplant-related charity at the end of the survey that will receive a \$1.50 donation (anonymously) if they complete the survey.

Sample size

Our target sample size is 122 participants. We expect that this will amount to approximately 61 participants per condition, although due to the nature of the randomization technique used (Qualtrics randomizer function), we may end up with slightly more or slightly less than 61 per condition.

Sample size rationale

A sample size of 61 per group was calculated to yield at least 90% power to detect a 30 percentage point difference between conditions (e.g., 35% vs. 65%) with $\alpha=0.05$ (GPower 3.1.9.4).

Stopping rule

We will stop data collection after the first of the following three scenarios is achieved: (1) 122 responses collected (2) August 31, 2020 and at least 100 responses collected (3) October 31, 2020.

Variables

Manipulated variables

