To test Hypotheses 1, we will use a binomial logistic regression analysis. The categorical independent variable will be 'stratified transplant survival'; the dependent variable is binary choice of hospital. -We will test whether the main effect of "stratified transplant survival" is statistically significant and in the predicted positive direction. To test Hypothesis 2, we will conduct a causal mediation analysis to determine whether information display had a mechanistic effect on hospital choice through our proposed mediator. We will estimate the average causal mediation effect (ACME), average direct effect (ADE), and the total effect. The ACME is the effect of the experimental information display condition (stratified) on the outcome of hospital choice (selective vs. non-selective), mediated through the hypothesized mediator (the importance of "getting any heart" at each hospital when considering the choice). The remaining effect of information display on hospital choice that is not mediated through the hypothesized mediator represents the ADE. The entire effect of the information display on hospital choice via the hypothesized mediator and the direct effect is the total effect. The proportion of the total effect that is accounted for by the ACME is called the proportion mediated.{Imai, 2010}. Analyses will be performed using the "mediation" package in R (The R Foundation for Statistical Computing).{Tingley, 2014}. We will generate 95% confidence intervals by using 1000 bootstrap simulations. The unstandardized point estimate of the ACME and its 95% confidence intervals will be interpreted. -A significant ACME for "stratified transplant survival" would suggest that stratifying transplant survival by number and quality of accepted donors works via increasing the perceived importance of "getting any heart" to increase preference for the non-selective hospital. If the ACME is non-significant, we will identify where the causal path breaks down. To test Hypothesis 3, we will conduct an analysis combining the data from the current study and the layperson study from the same two conditions in the previous study. We predict a 2 (information condition) x 2 (participant population) interaction, such that that effect of information condition is smaller for expert clinicians than for laypeople.

No files selected

Transformations

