Logistic regression analysis: The categorical predictor "transplant survival stratified" will be dummy coded (0=not stratified, 1=stratified), with 'stratified' as the reference category. The outcome variable "choice of hospital" will be dummy-coded (0=selective hospital, 1=non-selective hospital). The reference category is 'selective hospital'. Mediation analysis: The categorical predictor "transplant survival stratified" will be dummy coded (0=not stratified, 1=stratified), with 'stratified' as the reference category. The continuous mediator variable "get any heart" will be mean-centered for each analysis. The outcome variable "choice of hospital" will be dummy-coded (0=selective hospital, 1=non-selective hospital). The reference category is 'selective hospital'.

Inference criteria

We will use the standard $p=0.05$ criteria for determining if the results are significantly different from those expected if the null hypothesis were correct.

Data exclusion

n/a

Missing data

If a participant does not complete the entire survey, they will not be included in the analysis.

Exploratory analysis

No response

Other

Other

No response

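### The Hypothesis 2 rule for a non-significant ACME presumes a broken causal path and allows no inconclusive result, although the study was sized only for Hypothesis 1

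*Combined protocol and SAP*

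**What the plan says.** Under Statistical models, the ACME with a bootstrap interval is the test of Hypothesis 2: "We will generate 95% confidence intervals by using 1000 bootstrap simulations". The plan undertakes to interpret the ACME estimate together with that interval. A significant ACME is described cautiously, as suggesting mediation. For the opposite result the instruction is: "If the ACME is non-significant, we will identify where the causal path breaks down". No method for finding the break is given, and neither an inconclusive outcome nor a smallest mediated effect of interest is mentioned.

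The only general criterion is under Inference criteria: "We will use the standard $p=0.05$ criteria for determining if the results are significantly different" from what the null hypothesis predicts.

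The sample size rationale concerns choice of hospital alone: "A sample size of 61 per group was calculated to yield at least 90% power to detect a 30 percentage point difference between conditions", with 35% vs. 65% as the example. The stopping rule can close recruitment below 122: one limb is "August 31, 2020 and at least 100 responses collected", and the 31 October 2020 limb has no minimum.

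The Hypotheses section predicts both component paths, with no condition on the ACME: a higher rating in the stratified condition, and higher ratings going with choice of the non-selective center.

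**The concern.** A non-significant ACME can arise because a path is absent or because the data are too imprecise to show a real indirect effect. The sentence provides only for the first. An analyst who follows it faithfully has to name the link that failed, either condition to rating or rating to choice. If the link is picked because its own p-value exceeds 0.05, non-significance is read as absence a second time.

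At stake is a mechanistic conclusion. A report could say, for instance, that the stratified display does not change how much clinicians weigh the chance of getting any heart, when the data are compatible with a worthwhile change. This would apply even to a perfectly measured mediator.

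**Working it through.** **1. The plan's own figure.** Inputs from Sample size rationale: 35% vs. 65%, alpha 0.05, at least 90% power. Two-sided alpha is assumed, since sidedness is not stated.
- Pooled normal approximation: n = [1.96·√(2·0.5·0.5) + 1.2816·√(0.35·0.65 + 0.65·0.35)]² / 0.30² = (1.386 + 0.864)² / 0.09 = 56.3, so 57 per group.
- Two-sided Fisher exact power by enumeration: 89.2% at 60 per group and 90.07% at 61.

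The stated 61 is reproduced by the exact test. It covers Hypothesis 1 only.

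**2. Condition-to-rating path alone.** The documents give a 0–100 slider but no SD or expected shift, so the shift d in SD units is assumed. Power = Φ(d·√(n/2) − 1.96). For d = 0.4 and n = 61: Φ(0.4·5.523 − 1.96) = Φ(0.249) = 60%.

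| Shift (SD) | 61 per arm | 50 per arm |
|---|---|---|
| 0.3 | 38% | 32% |
| 0.4 | 60% | 52% |
| 0.5 | 79% | 71% |
| 0.6 | 91% | 85% |
| 0.8 | 99% | 98% |

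At 61 per arm a real shift of 0.3 or 0.4 SD has p>0.05 in 62% or 40% of trials.

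**3. The ACME, with assumed path strengths.** Model: condition X ~ Bernoulli(0.5); rating M = d·X + N(0,1); logit P(non-selective) = c·(X − 0.5) + ln(OR)·M, with c = 1. Percentile bootstrap interval, 500 draws, 600 trials per cell, Monte Carlo SE about 2 points. Both paths are truly non-zero. A false break is counted when the ACME interval includes 0 and at least one path has p>0.05. That way of locating a break is an assumption.

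| Scenario | N | ACME non-significant | False break |
|---|---|---|---|
| d 0.4, OR 1.8 per SD (true ACME about 5 points) | 122 | 51% | 293/600 = 49% |
| same | 100 | 60% | 331/600 = 55% |
| d 0.5, OR 2.0 per SD (true ACME about 7.5 points) | 122 | 27% | 153/600 = 26% |
| same | 100 | 44% | 247/600 = 41% |

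A separate run of the same model with 300 bootstrap draws gave 48% and 61% non-significant for the first scenario (250 trials per cell). For the second it gave 27% (1,800 trials; a smaller 250-trial run had given 41%) and 44% (250 trials).

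In these scenarios about 19% and 25% of the total effect is mediated. With strong mediation (d 0.8, OR 2.5, c = 0.6; total effect 27 points, 55% mediated) the ACME was non-significant in about 1% of 300 trials at N=122.

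**4. The ACME, with the total effect held at the planned 30 points.** Choice rates are fixed at 35% and 65%, with 1000 bootstrap draws and 600 trials per cell. The share mediated is assumed.

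| Share mediated | Shift (SD) | Power, 61 per arm | Power, 50 per arm |
|---|---|---|---|
| 25% | 0.3 | 42% | 35% |
| 25% | 0.4 | 59% | 49% |
| 25% | 0.5 | 72% | 60% |
| 25% | 0.8 | 60% | 47% |
| 50% | 0.5 | 78% | 72% |
| 50% | 0.6 | 92% | 85% |
| 50% | 0.8 | 99% | 96% |

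With 15% mediated, power at 61 per arm was 21–47% for shifts of 0.3 to 1.0 SD (200 trials per cell, SE up to 3.5 points). At a fixed share, power falls again for large shifts because the rating-to-choice link must then be weaker.

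Both models assume a normally distributed rating, a correctly specified choice model and no unmeasured confounding of rating and choice.

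**The case against.** The sentence can be read as an instruction to inspect the component paths. Nowhere does the plan say that a null ACME proves there is no mediation, and a reader who infers that goes beyond the text. The plan also commits to interpreting the ACME estimate with its interval, so imprecision would be visible, and it is cautious about a positive result. This stands as far as it goes. It does not cure the rule, because the instruction for a null result still directs the analysts to name a break.

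A reader might infer that path results will be reported only when the ACME is non-significant. The Hypotheses section does not support that, since both paths are predictions whatever the ACME shows.

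A reader might also infer that real mediation will often be missed. The documents give no rating SD, shift or association with choice, so no frequency can be derived from them. The miss rate is high for modest mediation and about 1% when mediation is strong. The false-break percentages further depend on locating the break by p-value, which the plan does not state. It is only the natural reading, given that p=0.05 is the sole criterion supplied.

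Finally, the documents offer no basis for a minimum relevant effect on either path, so setting one cannot be required.

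**Conclusion.** The point holds in limited form. The rule is triggered by non-significance, presupposes a break and names no inconclusive outcome, and Hypothesis 2 has no power basis at 61 per group. A modest real mediated effect could therefore be reported as a broken path.

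Under the assumed effects at N=122, the ACME would be non-significant in about 50%, 27% and 1% of trials for modest, moderate and strong mediation. With the total effect fixed at 30 points, the miss rate is roughly 40–80% for small-to-modest mediation, about 22–28% at a 0.5 SD shift with 25–50% mediated, and under 10% once the shift is 0.6–0.8 SD and half the effect is mediated. Stopping near 100 responses makes each of these worse.

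The wording defect comes from the documents themselves; its size rests on assumed mediator effects. Hypothesis 1 and its sample size are not in question.

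**What to change.** Replace the sentence under Statistical models with:

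> A non-significant ACME will be reported as inconclusive about mediation, with its 95% CI. The condition-to-rating effect and the rating-to-choice association (adjusted for condition) will be reported with 95% CIs, and no path will be described as absent or broken because its p-value exceeds 0.05.

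If the sponsor wants to be able to claim that a path is absent, it should state beforehand the smallest relevant effect that the path's interval must exclude, for example a difference in slider points or an odds ratio per 10 slider points. This is optional.

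The cost is a wording change with no extra data. The downside is that some Hypothesis 2 results will be labelled inconclusive instead of being assigned to a particular link.

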Don't Throw Your Heart Away: Clinician Study 3 Protocol

NCT04455893

Last IRB Check-In: Jan 10 2024

Study Information

Hypotheses

Hypothesis 1 When transplant centers present information on their transplant success rate only, evaluators will respond by selecting hospitals with higher transplant success. However, if information presented on transplant outcomes is stratified by the number and quality of donors used, or displayed in addition to total survival rates, then participants will respond by selecting hospitals with higher organ acceptance rates rather than the hospital with higher transplant outcomes. Thus, preference for the non-selective transplant center (relative to the selective center) will be lower in condition 1 (baseline: combined transplant survival only), compared to condition 2. That is, a higher proportion of participants will prefer the non-selective center over the selective center in condition 2, relative to condition 1. Hypothesis 2 The effect of information condition on choice will be mediated by ratings of the importance of getting a heart at all. That is, viewing information about stratified transplant survival will lead participants to think that the chance to "get a heart at all" is a more important factor in their decision which will in turn be associated with higher preference for the non-selective hospital. Specifically, ratings of importance (0-100 continuous scale) for the item "likelihood of getting any heart" will be lower in condition 1 than in condition 2. Furthermore, ratings on this item will be associated with choice, such that higher ratings will be associated with choice of the non-selective center. A bootstrapped mediation analysis will test for an indirect effect. Hypothesis 3 The difference in hospital preference between the treatment (stratified transplant survival) and control (combined transplant survival) conditions for the clinician participants will be smaller than the analogous difference observed in a previous study of layperson (Amazon Mechanical Turk) participants exposed to the same two conditions. In an analysis combining the data from the current study and the layperson study from the same two conditions in the previous study, we predict a 2 (information condition) x 2 (participant population) interaction, such that that effect of information condition is smaller for expert clinicians than for lay people.

Design Plan

Study type

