Experiment - A researcher randomly assigns treatments to study subjects, this includes field or lab experiments. This is also known as an intervention experiment and includes randomized controlled trials.

Blinding

- For studies that involve human subjects, they will not know the treatment group to which they have been assigned.

Is there any additional blinding in this study?

n/a

Study design

We have a between-subjects design in which participants are randomized to one of two information conditions (independent variable). In each condition, they make a choice (dependent variable) between two hospitals (one with a non-selective donor acceptance strategy, and another with a more selective donor acceptance strategy). Independent variables: (1) Condition 1 ("baseline" condition): view only combined transplant survival (e.g. transplant

survival rate not stratified by number and quality of donor hearts accepted at each center) (2) Condition 2: view only stratified transplant survival (e.g. transplant survival rate stratified into patients who received excellent donor organs and patients who received less than optimal donor organs) These two conditions will be analyzed for our primary analysis: a 1x2 design with 2 arms (control arm or combined transplant survival, and experimental arm or stratified transplant survival).

Randomization

We will use simple randomization, where each participant will be randomly assigned to one of the two predetermined conditions. The Qualtrics randomizer function will be used for randomization into a condition.

Sampling Plan

Existing Data

Registration prior to creation of data

Explanation of existing data

n/a

Data collection procedures

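### Does Hypothesis 3 need a stated model and effect scale before its condition-by-population interaction can be tested?

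*Combined protocol and SAP*

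**What the plan says.** Under Hypotheses, the third hypothesis begins: "The difference in hospital preference between the treatment (stratified transplant survival) and control (combined transplant survival) conditions for the clinician participants will be smaller". The comparator is the result in laypeople, which the same sentence describes as "the analogous difference observed in a previous study of layperson (Amazon Mechanical Turk) participants exposed to the same two conditions". Under Statistical models, the two data sets are to be combined, and the prediction is worded: "We predict a 2 (information condition) x 2 (participant population) interaction, such that that effect of information condition is smaller for expert clinicians". No model, link or effect measure is given for this test.

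The other two hypotheses are specified more fully. For the first: "To test Hypotheses 1, we will use a binomial logistic regression analysis". For the second: "We will estimate the average causal mediation effect (ACME), average direct effect (ADE), and the total effect", with the software and the bootstrap named.

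Transformations codes condition (it "will be dummy coded (0=not stratified, 1=stratified") and hospital choice. It does not code participant population. Inference criteria sets a single rule for the whole plan, p=0.05, as the "criteria for determining if the results are significantly different from those expected if the null hypothesis were correct". Under Existing Data the entry is "Registration prior to creation of data", and the explanation field is marked not applicable.

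**The concern.** The outcome is a choice between two hospitals, so an interaction depends on the scale on which it is measured. A smaller difference in proportions and a smaller odds ratio are in general different statements, and data can support one without the other. The plan's wording points both ways. Hypothesis 3 speaks of a difference in preference, which suggests proportions, while the only regression named for hospital choice is logistic, which works in odds ratios. A 5% significance rule therefore applies to a test that is not fully defined.

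If the analysts could choose the scale after seeing the counts, Hypothesis 3 might be called supported when the other scale would not support it, or the reverse. The layperson result was already known when the plan was written, so the layperson half of the comparison could have guided the choice. A missing code for participant population looks like a further gap.

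**Working it through.** **The plan's own figure.** The only sample-size figure is 61 per group, for 35% vs 65% at two-sided 5% with at least 90% power (Sample size rationale). It concerns Hypothesis 1. Exact power of Fisher's test is 0.892 at 60 per group and 0.901 at 61, so the figure reproduces. Nothing comparable is stated for Hypothesis 3.

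**Inputs.** Clinicians: 61 per condition (Sample size). Laypeople: neither rates nor sample size are given, so both are assumed. The main figures use 200 per condition, with 61 and 400 as the range.

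**Formulas.** Subscripts 0 and 1 are the combined and stratified conditions; C is clinicians and L laypeople.

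- Difference of risk differences: d = (pC1 − pC0) − (pL1 − pL0), with SE = √Σ p(1 − p)/n over the four cells.
- Ratio of odds ratios: L = ln(ORC/ORL), with SE = √Σ(1/count) over the eight counts (choosers and non-choosers).
- Each is tested by z = estimate/SE, two-sided.

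**Set A:** laypeople 120/200 → 180/200, clinicians 30/61 → 40/61.

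- d = 0.164 − 0.300 = −0.136. SE = √(0.00120 + 0.00045 + 0.00410 + 0.00370) = 0.097. z = −1.40, p=0.16.
- ORL = (180×80)/(20×120) = 6.00. ORC = (40×31)/(21×30) = 1.97. Ratio 0.33, L = −1.115. SE = √(1/120 + 1/80 + 1/180 + 1/20 + 1/30 + 1/31 + 1/40 + 1/21) = 0.463. z = −2.41, p=0.016.

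Two further sets, by the same formulas:

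| Set | Laypeople | Clinicians | d (points) | p | Ratio of odds ratios | p |
|---|---|---|---|---|---|---|
| B | 70/200 → 130/200 | 46/61 → 54/61 | −16.9 | 0.043 | 2.52/3.45 = 0.73 | 0.56 |
| C | 130/200 → 190/200 | 21/61 → 40/61 | +1.1 | 0.90 | 3.63/10.23 = 0.35 | 0.047 |

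So the scale can decide whether Hypothesis 3 is called supported. In each set the contrast is between a significant and a non-significant result. None shows significant effects in opposite directions.

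**Population coding.** Relabelling a two-level factor changes the sign or size of the interaction coefficient and its SE together, so z keeps its magnitude. In a refitted example the logistic interaction gave p=0.4661 under all four codings tried. The missing code cannot affect the verdict.

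**When the scales agree.** Differing rates do not by themselves force a conflict. A rise from 20% to 50% and one from 50% to 80% are both 30 points, and both have odds ratio 4.0: (0.5/0.5)/(0.2/0.8) and (0.8/0.2)/(0.5/0.5).

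**How often they disagree.** These are simulations with a layperson effect of +30 points, a clinician effect of +15 points and 200 laypeople per condition.

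- Laypeople 35% → 65%, clinician baseline 30% to 55%: verdicts differ in about 1 to 6% of runs.
- Laypeople 35% → 65%, clinicians 75% → 90%: power is 45% for the risk-difference test and 5% for the logistic test (29–52% and 4–5% for 61 to 400 laypeople).
- Laypeople 60% → 90%, clinicians 50% → 65%: 34% and 72% (26–36% and 48–79%).
- All 208 baseline pairs (laypeople 5–65%, clinicians 5–80%, steps of 5): median disagreement 23% (14–27%). Restricted to the 62 pairs with baselines within 10 points, it is about 11%.

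**Validity.** With 35% → 65% in both populations there is no interaction on either scale. The two tests then reject in the predicted direction in 2.4% and 2.5% of runs, as they should.

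**The case for a change.** The strongest case for a change is that a registered hypothesis should have one defined test, and this one does not. Logistic regression is named for Hypothesis 1 only, and a reader who carries it over tests something other than the plain sense of a difference in preference. The consequences can be large. With equal risk differences (laypeople 65% → 95%, clinicians 35% → 65%) the logistic test supports Hypothesis 3 in 55% of runs, against 2% for the risk-difference test. With equal odds ratios (laypeople 35% → 65%, clinicians 80% → 93.2%) the figures are 3% and 59%. The remedy would be two or three sentences.

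The omission itself stands, and so does the arithmetic. What does not follow is that the plan lacks a usable test. Hypothesis 1 is also worded in proportions and is tested by logistic regression, so similar wording in Hypothesis 3 does not signal a different model. The logistic coding in Transformations is not restricted to Hypothesis 1. Adding population and a product term to that model is the natural reading, though it is an inference. The extreme scenarios need baselines far apart or rates near 90 to 95%, and nothing in the documents indicates either.

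The Existing Data entry adds little. The earlier layperson study is openly disclosed in both Hypotheses and Statistical models, and the entry can be read as covering the clinician data yet to be collected. Nothing shows that a scale was chosen after the fact. Listing the layperson counts would be helpful, but it does not settle which scale to use.

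**Conclusion.** The concern is accurate as an observation but does not require a change. The plan leaves out the model and scale for Hypothesis 3, and with a binary outcome that can move a result across 5%, as sets A to C show. The gap is one that analysts would fill sensibly from the plan itself, by logistic regression with condition, population and their product, and that test is valid. Asking the authors to write down a scale while leaving the choice to them corrects no error. Reporting both scales is a reasonable preference, and not a condition for a sound analysis. The product model is also saturated, so the four cell counts determine both contrasts, and anyone given those counts can compute the other one.

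Every figure for the frequency of disagreement rests on assumed layperson rates, layperson numbers and effect sizes. Over those assumptions it runs from about 1% of studies, when both populations have similar mid-range rates, to a median of 23% over a wide grid that weights implausible and plausible pairs alike. The primary analysis and the sample size of 61 per group are unaffected.

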The outcome variable will be a binary choice between two hospitals: one with a selective donor-heart acceptance strategy and one with a non-selective donor heart acceptance strategy. Participants will respond to the question "Which Hospital do you consider to be higher performing? Please click on one of the two tables below to indicate which hospital is the better choice." Participants will choose between two outcome tables featuring the selective and non-selective hospital (counterbalanced, such that each of the two choices is equally likely to be presented at top of the choice scenario in each condition). The number of participants that choose each hospital will be the measured outcome variable used in analyses. On the next page of the survey, participants will respond to three mediator questions: "There are many reasons why one transplant hospital might outperform another. Which reasons were most important in your decision? Please move the slider to indicate how much you considered each of the reasons below (0=reason was not important, 100=reason was extremely important)." Participants will then move a slider bar (0-100) to indicate the importance of the following three items: (1) Patients were more likely to receive an excellent donor heart at the hospital I picked. (2) Patients were less likely to receive a marginal donor heart at the hospital I picked. (3) Patients were more likely to receive any kind of heart at the hospital I picked. The third item (more likely to receive any kind of heart) will be the only variable that is included in the planned mediation analysis.

Indices

n//a

No files selected

Analysis Plan

Statistical models

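### The completers-only rule discards recorded hospital choices from the Hypothesis 1 analysis and conditions a randomised comparison on an event that follows the outcome

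*Combined protocol and SAP*

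**What the plan says.** - **Exclusion rule** (Analysis Plan, Missing data): "If a participant does not complete the entire survey, they will not be included in the analysis". No exception is made for any hypothesis. The Data exclusion entry is marked not applicable, and no section gives Hypothesis 1 its own analysis set.
- **Outcome** (Variables, Measured variables): "The outcome variable will be a binary choice between two hospitals".
- **Order of questions** (same section): the choice comes first, then "On the next page of the survey, participants will respond to three mediator questions". Of those items, the any-heart rating "will be the only variable that is included in the planned mediation analysis".
- **Hypothesis 1 model** (Analysis Plan, Statistical models): "To test Hypotheses 1, we will use a binomial logistic regression analysis", in which "the dependent variable is binary choice of hospital" and the predictor is condition. No mediator enters.
- **Last step of the survey** (Sampling Plan, Data collection procedures): "Participants will be given the option to select a transplant-related charity at the end of the survey". The donation is made only if the survey is completed.
- **Stopping rule** (Sampling Plan): the first two conditions read "1) 122 responses collected (2) August 31, 2020 and at least 100 responses collected". The plan does not say whether an incomplete survey counts as a response.

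**The concern.** Someone who was randomised, saw the display, chose a hospital and left at the slider page or the charity option has nothing missing for Hypothesis 1. The plan still removes that person.

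More is at stake than a few lost records. Randomisation protects the comparison of everyone assigned. Completion comes after the display and after the choice, so it can depend on both, and a comparison among completers no longer has that protection. The dependence is conceivable here. The sliders ask about excellent, marginal and any hearts at the hospital picked, while only the stratified arm saw survival split by donor quality. How well the items fit a respondent may therefore vary with arm and choice together. That is inference from the design, not evidence of bias. The plan asks for no count of non-completers by arm, so a reader could not judge whether the problem was negligible.

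A second, conditional issue is power. If recruitment stops at 122 responses and some are incomplete, the analysed sample falls short of the 61 per arm on which the power statement rests.

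**Working it through.** **Inputs from the plan:** 61 per arm; 35% vs 65% choosing the non-selective hospital; alpha 0.05 (taken as two-sided, since sidedness is not stated); power of at least 90%.

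**Assumed:** all rates of quitting after the choice, because the documents give none.

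**1. The plan's own figure.** The power of the two-sided Fisher exact test, by enumeration, is 0.892 at 60 per arm and 0.901 at 61. So 61 is the first size in the range checked (57 to 64) to reach 90%. The uncorrected z test gives 0.922 at 61. The sample size is reproduced and is not in dispute.

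**2. Effect of conditioning on completion.** Let p be the true proportion choosing the non-selective hospital in an arm, and q_non and q_sel the quit rates after each choice in that arm. Among completers:

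observed p = p(1 − q_non) / [p(1 − q_non) + (1 − p)(1 − q_sel)]

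observed OR = true OR × [(1 − q_non,strat)(1 − q_sel,comb)] / [(1 − q_sel,strat)(1 − q_non,comb)]

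The true OR is (0.65/0.35)/(0.35/0.65) = 3.449. If quitting depends on arm only, or on choice only, the factors cancel and the OR stays at 3.45. Bias in the OR needs a choice-quitting relation that differs by arm.

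With 5% quitting everywhere except in one stratified-arm choice group:

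| Quit rate in that group | Group | Observed difference (true 30 points) | OR multiplier | Observed OR |
|---|---|---|---|---|
| 10% | selective choosers | 66.2% − 35.0% = 31.2 points | 0.95/0.90 | 3.64 |
| 10% | non-selective choosers | 63.8% − 35.0% = 28.8 points | 0.90/0.95 | 3.27 |
| 20% | selective choosers | 68.8% − 35.0% = 33.8 points | 0.95/0.80 | 4.10 |
| 20% | non-selective choosers | 61.0% − 35.0% = 26.0 points | 0.80/0.95 | 2.90 |

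**3. Under a 50/50 null.** In the 20% case the stratified arm shows 54.3% or 45.7% against 50.0%, a spurious 4.3 points (OR 1.19 or 0.84). Expected completers are 61 × 0.95 = 57.9 in the combined arm and 61 × (0.5 × 0.80 + 0.5 × 0.95) = 53.4 in the stratified arm. The standard error is then about 9.5 points, and the two-sided z test rejects with probability 0.0735. In the 10% case the shift is 1.4 points and the rejection probability is 0.052.

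**4. Power, only if the 122 responses include incomplete surveys.** A share d quits after choosing, leaving 61(1 − d) per arm (rounded to a whole number for the Fisher test):

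| d | n per arm | z test | Fisher exact |
|---|---|---|---|
| 0 | 61 | 92.2% | 90.1% |
| 5% | 58 | 90.8% | 87.4% |
| 10% | 55 | 89.3% | 84.2% |
| 20% | 49 | 85.4% | 81.4% |

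For scale, the plan's own permitted stop at 100 responses (50 per arm) gives 86.2% by z test. If instead 122 means completed surveys, planned power is kept. Adding the quitters' choices would then raise the sample to 61/(1 − d), or about 64, 68 or 76 per arm for d = 5%, 10% or 20%, with z-test power of 93.4%, 94.6% or 96.6%.

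**The case against.** The best case for leaving the rule alone is that the harm is hypothetical. The only steps described after the choice are one page of three sliders and a charity option, and the donation rewards finishing. At twofold differential quitting (10% against 5%), type I error is 5.2%, which is trivial. The 7.3% figure needs a fourfold rate confined to one choice group in one arm, and even then the shift is under half a standard error. This stands, and it is why the point is a recommended change and not a fatal flaw.

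The power loss is also unproven. The target is 122 participants, the recruitment text mentions 125, and non-completers are not analysed, so 122 completed surveys is a natural reading. That stands too: the loss is conditional on the other reading.

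The remedy is partial. People who quit before choosing remain excluded, and having a recorded choice is itself a post-randomisation condition. This is true, but it is no reason to discard choices that were observed.

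There may be costs. With several recruitment routes and no described check for duplicates, someone who abandons and restarts could be counted twice. Use of partial data may also depend on consent wording that is not shown. Both are conjecture, worth checking but not decisive.

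Finally, a single complete-survey set keeps Hypothesis 1 and the Hypothesis 2 total effect on the same people. That is a real convenience, and it can be kept as a sensitivity analysis.

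**Conclusion.** The concern holds. The exclusion is unqualified, the choice precedes the slider page, and the Hypothesis 1 model needs only condition and choice. As written, the plan drops any complete Hypothesis 1 data from later quitters and conditions the primary randomised comparison on an event after the outcome.

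The existence of the defect rests on the text alone; its size rests on assumed quit rates. Under the rates examined, a true 30 points appears as anything from 26.0 to 33.8 points, and type I error is between 5.2% and 7.3%. There is no bias in the odds ratio if quitting depends on arm only or on choice only. Loss of power depends on an unstated definition of a response. The plan should be changed because the change is cheap and the plan offers no way to check afterwards that the effect was small.

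**What to change.** Replace the Missing data rule with text such as:

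> The primary Hypothesis 1 analysis includes every randomised participant with a recorded hospital choice, whether or not the rest of the survey was completed. The Hypothesis 2 analysis includes those who also rated the any-heart item. The Hypothesis 1 result in the Hypothesis 2 set is reported as a sensitivity analysis.

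In addition:

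- Report by arm the numbers randomised, with a recorded choice, and completing. Those lost before the choice cannot be recovered but will be visible.
- State in the stopping rule whether a response means a completed survey.
- For Hypothesis 3, apply the same inclusion rule to the clinician and layperson data where the layperson data allow it. Otherwise use the layperson study's rule for both populations. That rule is not in the documents.
- Confirm that the survey platform keeps partial responses, that the consent covers their use, and how repeat entries would be recognised.

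The cost is a few sentences and one count table. The downside is that Hypothesis 1 and the Hypothesis 2 total effect may rest on slightly different participants, which the sensitivity analysis makes visible. If partial responses were not kept, the main change cannot be made; the definition of a response is still needed, as are whatever counts by arm the records allow.
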